10.3 Vital Signs

Descriptive statistics for vital signs (eg, supine pulse rate, supine systolic and diastolic BP, body weight) values at baseline and changes from baseline values at each assessment visit, and at the end of the Open-label Treatment Period will be presented.

Vital sign values will be considered PCS if they meet the criteria for both the observed value and the change from baseline value listed in Table 10-4. The number and percentage of patients with PCS postbaseline vital sign values during Open-label Treatment Period will be tabulated for the Safety Population. The percentages will be calculated relative to the number of patients with an available baseline value and at least 1 postbaseline assessment. The numerator will be the total

Confidential Page 22 of 40

number of patients with an available baseline value and at least 1 PCS postbaseline vital sign value. A supportive listing of patients with PCS postbaseline values will be provided and will include the PID number and baseline and postbaseline values for each patient. A listing of all AEs for patients with PCS vital sign values will also be provided.

Table 10-4: Criteria for Potentially Clinically Significant Vital Signs

Vital Sion Danameter mit	Elaa	Criteria ^a					
Vital Sign Parameter, unit	Flag	Observed Value	Change From Baseline				
Supine Systolic blood pressure, mmHg	High	≥ 180	Increase of ≥ 20				
Supine Systone blood pressure, mining	Low	≤ 90	Decrease of ≥ 20				
Suning Digetalia blood procesure, mmHg	High	≥ 105	Increase of ≥ 15				
Supine Diastolic blood pressure, mmHg	Low	≤ 50	Decrease of ≥ 15				
Supine Pulse rate, bpm	High	≥ 120	Increase of ≥ 15				
Supine Fuise rate, opin	Low	≤ 50	Decrease of ≥ 15				
Waighth	High	_	Increase of ≥ 7%				
Weight ^b	Low	_	Decrease of ≥ 7%				

bpm = beats per minute.

The number and percentage of patients with orthostatic hypotension during the Open-label Treatment Period will be provided for the Safety Population. Orthostatic hypotension is defined as a reduction of ≥ 20 mm Hg in SBP or a reduction of ≥ 10 mm Hg in DBP while changing from the supine to standing position. A supportive listing of patients with orthostatic hypotension during the Open-label Treatment Period and Safety Follow-up Period will be provided. A listing of all AEs occurring in patients who experienced orthostatic hypotension will also be provided.

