6.1 Overall Study Design and Plan

Study ITI-007-503 ("Study 503") is an international, open-label, multicenter, 6-month study to assess the safety and tolerability of lumateperone as adjunctive therapy in patients with MDD. The Study will be performed at approximately 120 study centers. No *de novo* patients will be enrolled.

Patients who have safely completed the lead-in studies may be eligible to participate in this Openlabel Safety Study. Lead-in study completion is defined as a patient who completes the doubleblind treatment period (ie, all scheduled visits up to and including Visit 8) of the lead-in study.

The study will be conducted as follows:

- A **Screening Period** of one day in duration. Potential patients rolling over from the leadin studies will be evaluated for eligibility during the Screening/Baseline Visit (Visit 1/Day 1) which is the same visit as Visit 8/Day 43 of the lead-in study. Patients who meet all eligibility criteria at the Screening/Baseline Visit (Visit 1/Day 1) will be dispensed lumateperone 42 mg to be self-administered each evening without respect to food.
- A **26-week Open-label Treatment Period** during which patients will self-administer lumateperone, to be taken each evening, without respect to food. Background ADT should also continue as previously prescribed, with no change of dose from the lead-in studies. Patients will attend visits on Weeks 1, 2, 3, 4, 6, 8, 10, 12, 14, 16, 18, 20, 22, 24, and 26. The Open-label Treatment Period will last a total of 26 weeks. A patient will be defined as a treatment completer if the patient completes the Open-label Treatment Period (all scheduled visits up to and including Visit 16/Week 26).
- A 2-week Safety Follow-up Period. A Safety Follow-up visit will occur approximately 2 weeks after completion of the Open-label Treatment Period or after the Early Termination (ET) Visit. Any ongoing AEs at the Safety Follow-up Visit must be followed until resolution, until the AE stabilizes, until it is determined to be not clinically significant, or until the patient is lost to follow-up.

Patients who prematurely discontinue should be seen for an ET visit as soon as possible and will also be asked to return to for a Safety Follow-up visit approximately 2 weeks after Visit 16/ET visit.

The maximum per-patient study duration for the Open-label Safety Study will be approximately 28 weeks.

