8.2.5 Vital Signs

Vital signs (pulse rate, systolic and diastolic blood pressure [BP], body temperature, and body weight) will be assessed at every visit during the study as specified in the Schedule of Evaluations (Table 1-1). Height and BMI are assessed at the Screening/Baseline Visit (Visit 1/Day 1) only; waist circumference will be assessed at Screening/Baseline (Visit 1/Day 1) and Visit 16/ET.

Blood pressure and pulse rate will be measured twice: once after the patient is resting quietly in the supine position followed by once after at least 2 minutes in the standing positions. BP may be measured either manually or by machine but using the same method consistently for each patient throughout the study.

Patients should be kept as calm and undisturbed as possible while BP and pulse rate measurements are taken (eg, there should be no talking while the BP is being measured). The same arm and BP cuff (appropriate to the arm circumference) should be used for all BP measurements.

Whenever possible, the patient's weight should be measured at the same time of day; the patient should wear his/her usual indoor clothing without jacket and shoes. For each patient, body weight and height should be determined using the same equipment during the study after ensuring its proper calibration.

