9.2 CGI-S Score

A descriptive summary for the change from baseline to each assessment visit in CGI-S score will be provided for each scheduled visit.

Confidential Page 17 of 40

10. SAFETY ANALYSES

Safety analyses will be performed using the Safety Population. The safety parameters will include AEs, clinical laboratory, vital signs, ECG, and EPS (AIMS, BARS, and SAS) and C-SSRS scales. Baseline is defined as the last measurement prior to the first dose of double-blind treatment during the lead-in studies (Studies ITI-007-501 and ITI-007-502).

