10.2 Clinical Laboratory Parameters

Descriptive statistics for clinical laboratory values (in SI and conventional units) and changes from baseline values at each assessment timepoint and at the end of the Open-label Treatment Period will be summarized for each clinical laboratory parameter:

- **Hematology:** hematocrit; hemoglobin; red blood cell count with indices (mean corpuscular volume, mean corpuscular hemoglobin, and mean corpuscular hemoglobin concentration); reticulocytes; white blood cell count and differential (neutrophils, lymphocytes, monocytes, eosinophils, and basophils) reported as percent (%) and absolute values; and platelet count.
- Chemistry: albumin; alkaline phosphatase; ALT; AST; bilirubin (total, direct); blood urea nitrogen; calcium; chloride; cholesterol (high-density lipoprotein [HDL] and low-density lipoprotein [LDL] will be calculated and reported); creatinine; creatine phosphokinase; gamma-glutamyl transferase; glucose; insulin; lactate dehydrogenase; phosphate; potassium; prolactin; sodium; triglycerides; total protein; uric acid; HbA1c; and TSH (reflex free T3 and free T4).
- Urinalysis: pH and specific gravity.

Clinical laboratory values are considered potentially clinically significant (PCS) values if they meet either the lower or upper criteria listed in Table 10-2. The number and percentage of patients with PCS postbaseline clinical laboratory values during Open-label Treatment Period will be tabulated. The percentages will be calculated relative to the number of patients with available non-PCS baseline values and at least 1 postbaseline assessment. The numerator will be the total number of patients with available non-PCS baseline values and at least 1 PCS postbaseline value during the Open-label Treatment Period. A supportive listing of patients who have PCS values will be provided and will include the PID number and baseline and postbaseline values for each patient. A listing of all AEs for patients with PCS clinical laboratory values will also be provided.

Confidential Page 20 of 40

Table 10-2: Criteria for Potentially Clinically Significant Clinical Laboratory Tests

Laboratory Parameter	Conventional Unit	PCS Criteria ^a Low Values	PCS Criteria ^a High Values		
Hematology					
Hemoglobin	g/dL	< 0.9 × LLN	_		
Hematocrit	%	< 0.9 × LLN	_		
Absolute neutrophil count (ANC)	10^3/μL	< 1.0	_		
Platelet count	10^3/μL	≤ 75	≥ 700		
White blood cell (WBC) count	10^3/μL	≤ 2.5	≥ 15		
Chemistry					
Albumin	g/dL	< 2.5			

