10.4 Electrocardiograms

Descriptive statistics for ECG parameters (eg, ventricular heart rate, QTc interval, QRS interval) at baseline and changes from baseline values at each assessment visit, and at the end of the Openlabel Treatment Period will be summarized.

ECG parameter values will be considered PCS if they meet the criteria listed in Table 10-5. The number and percentage of patients with PCS postbaseline values during Open-label Treatment Period will be tabulated for the Safety Population. The percentages will be calculated relative to the number of patients with baseline value (for criteria involving change from baseline) or non-PCS baseline value (for criteria not involving change from baseline), and at least 1 assessment during the open-label treatment period. The numerator will be the total number of patients out of those included in the denominator and with at least 1 PCS value during the Open-label Treatment Period. A supportive listing for all patients with PCS values will be provided, which will include the PID number and baseline and postbaseline ECG values for each patient. A listing of all AEs for patients with PCS ECG values will also be provided.

Confidential Page 23 of 40

^a A postbaseline value will be considered potentially clinically significant if it meets both criterion value and change from baseline.

b Weight change is relative to baseline.

Table 10-5: Criteria for Potentially Clinically Significant Electrocardiographic Values

D	Criteria ^a							
Parameter, unit	Value	Change from Baseline						
QRS duration, msec	≥ 150	_						
PR interval, msec	≥ 250	_						
QTcB, msec	≥ 480	_						
QTcB, msec	≥ 500	_						
QTcF, msec	≥ 480	_						
QTcF, msec	≥ 500	_						
QTcB, msec	_	> 30 and ≤ 60						
QTcB, msec	_	Increase of > 60						
QTcF, msec	_	> 30 and ≤ 60						
QTcF, msec	_	Increase of > 60						

PCS = potentially clinically significant; QTc = corrected QT interval; QTcB = QT interval/(RR)½; QTcF = QT interval/(RR)½.

Confidential Page 24 of 40

^a A post-baseline value will be considered potentially clinically significant if it meets the criterion value or the change from baseline value.

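### SAP 10.3 counts orthostatic hypotension over the open-label period with no baseline condition, no stated denominator and no baseline or by-visit rate, so the percentage cannot be read as treatment-emergent

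*SAP*

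**What the plan says.** The output is defined in SAP 10.3 (Vital Signs): "The number and percentage of patients with orthostatic hypotension during the Open-label Treatment Period will be provided for the Safety Population". The criterion follows: "Orthostatic hypotension is defined as a reduction of ≥ 20 mm Hg in SBP or a reduction of ≥ 10 mm Hg in DBP" on moving from supine to standing. It uses two readings from the same visit and has no change-from-baseline part.

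The neighbouring analyses all bring in baseline:

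- Laboratory values (SAP 10.2): "The percentages will be calculated relative to the number of patients with available non-PCS baseline values and at least 1 postbaseline assessment".
- ECG (SAP 10.4): criteria based on a value alone need a "non-PCS baseline value (for criteria not involving change from baseline), and at least 1 assessment during the open-label treatment period".
- Other vital signs (SAP 10.3): apart from weight, which is judged on percentage change alone, a value is PCS only if it meets both a level and a change from baseline. Numerator and denominator are both defined.

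The measurement schedule is in the protocol. Section 8.2.5: "Vital signs (pulse rate, systolic and diastolic blood pressure [BP], body temperature, and body weight) will be assessed at every visit during the study", and "Blood pressure and pulse rate will be measured twice: once after the patient is resting quietly in the supine position followed by once after" a stand of 2 minutes or more. Section 6.1: "Patients will attend visits on Weeks 1, 2, 3, 4, 6, 8, 10, 12, 14, 16, 18, 20, 22, 24, and 26". Baseline for safety is set at the start of SAP Section 10: "Baseline is defined as the last measurement prior to the first dose of double-blind treatment during the lead-in studies".

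**The concern.** Orthostatic hypotension is the kind of criterion for which SAP 10.4 asks for a non-PCS baseline: a threshold with no reference to an earlier value. Here that condition is absent and nothing explains the difference. A patient who met the criterion before any study drug and meets it again once during open-label treatment is counted like a patient in whom it is new.

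Two further gaps make the figure hard to interpret. The SAP does not say that one positive reading is enough, though that is the natural meaning, and it does not say who is in the denominator. It also plans no percentage at baseline or by visit. The PCS listings must show baseline values; the orthostatic listing carries no such requirement.

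Safety and tolerability is the primary objective, and there is no control arm to show the background. What is at stake is whether a reader can separate background from new findings in this row.

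**Working it through.** The documents state no orthostatic hypotension rate, so there is no figure to reproduce. The check asks how large each source of background could be with no drug effect.

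**Inputs from the documents.** Open-label visits after Visit 1: Weeks 1, 2, 3, 4, 6, 8, 10, 12, 14, 16, 18, 20, 22, 24 and 26, that is Visits 2 to 16, or 15 visits. Planned enrolment is about 760.

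**Assumptions, not from the documents.** Chance p of meeting the criterion at any one visit, the same at baseline and throughout; within-patient correlation ρ between visits; one baseline reading; full attendance.

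**Step 1. Accumulation with independent visits.** P(at least one positive in 15) = 1 − (1 − p)^15.

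- p = 1%: 14.0%
- p = 2%: 26.1%
- p = 3%: 36.7%
- p = 5%: 53.7%

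Under independence the baseline reading carries no information about later visits. Removing baseline-positive patients leaves these figures unchanged: 53.7% before and 53.7% after at p = 5%.

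**Step 2. Accumulation with correlated visits.** In a beta-binomial model with a = p(1 − ρ)/ρ and b = (1 − p)(1 − ρ)/ρ, the chance of no positive in k readings is P0(k) = B(a, b + k)/B(a, b). Then

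- ever positive = 1 − P0(15);
- ever positive among baseline-negative patients = 1 − P0(16)/(1 − p).

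Example, p = 5% and ρ = 0.3: a = 0.117, b = 2.217, P0(15) = 0.7706, P0(16) = 0.7654. Ever = 22.9%, or about 174 of 760. Baseline-free = 1 − 0.7654/0.95 = 19.4%. Gap = 3.5 points.

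| p | ρ | Ever positive | After removing baseline-positive patients | Gap (points) | Share of ever cases positive at baseline |
|---|---|---|---|---|---|
| 2% | 0.3 | 9.8% | 8.2% | 1.6 | 18% |
| 2% | 0.7 | 4.3% | 2.4% | 1.9 | 46% |
| 5% | 0.1 | 37.2% | 35.1% | 2.1 | 10% |
| 5% | 0.3 | 22.9% | 19.4% | 3.5 | 20% |
| 5% | 0.7 | 10.4% | 5.9% | 4.6 | 47% |
| 5% | 0.9 | 6.6% | 1.7% | 4.9 | 75% |

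**Step 3. A bound that does not need the model.** Among patients with a baseline reading and at least one open-label reading, splitting the ever rate by baseline status gives

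gap = p × [P(ever | positive at baseline) − P(ever | negative at baseline)],

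where p is the baseline prevalence. The bracket cannot exceed 1, so the gap cannot exceed p. For p = 5% and ρ = 0.3: 0.05 × (0.896 − 0.194) = 0.035, matching the table.

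There are thus two separate components. Baseline-positive patients add at most p percentage points. The rest of the no-drug rate comes from 15 readings being set against one, and a baseline exclusion does not touch it.

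**The case against.** The strongest reply is that the row is descriptive and does what its label says. The SAP uses the term treatment-emergent for AEs and liver values and does not use it here. No test or attribution is attached. Orthostatic events reported as AEs pass through the TEAE definition, and patients with orthostatic hypotension are listed with their AEs. This stands to the extent that the row is not a numerical error and not the only evidence on the question. But none of these outputs supplies a baseline rate, and the departure from SAP 10.2 and 10.4 remains unexplained.

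Several stronger readings are tempting, and the documents do not support them.

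- *The 14% to 54% in Step 1 is the error from keeping baseline-positive patients.* It is not. Those figures measure accumulation and survive the exclusion intact.
- *Correlation means most cases were already positive at baseline.* In the table they are a minority up to ρ = 0.7 and a majority only at ρ = 0.9, where the ever rate is itself low.
- *The denominator is the whole Safety Population.* The SAP uses the same phrase for PCS vital signs and PCS ECG values and then narrows the denominator. For orthostatic hypotension it is simply not specified.
- *The rate will overstate the drug's effect.* It can. If patients without paired readings are kept in the denominator, that pulls the other way.
- *A pre-drug rate is already available.* The SAP baseline precedes the first lead-in dose, and these documents do not confirm a standing blood pressure there. Paired readings are confirmed only within this study. Its Visit 1 is Day 43 of the lead-in study, when some patients may already be taking lumateperone (protocol 6.2.1 speaks of patients starting or continuing it).

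Fifteen visits is also the scheduled number. Early terminations reduce it, and the remote visits allowed under protocol Table 1-1 may reduce the number of paired readings.

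**Conclusion.** The point holds as a gap in interpretation and consistency. As written, the SAP 10.3 percentage mixes patients who met the criterion before drug, background readings accumulated over up to 15 scheduled visits, and any drug effect. It gives the reader no means of separating them.

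The part due to baseline-positive patients is at most the baseline prevalence in percentage points: 2.1 to 4.9 points at an assumed 5% with ρ from 0.1 to 0.9. Accumulation can be larger, but it calls for baseline and by-visit percentages rather than an exclusion alone. All rates rest on assumed p and ρ, constant risk, no drug effect and full attendance, so the true size cannot be taken from the documents. The change is worth making because the row serves the primary objective and the correction is inexpensive.

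**What to change.** In SAP 10.3:

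1. Keep the crude row and define it. Numerator: patients with at least one paired supine/standing reading in the Open-label Treatment Period that meets the criterion. Denominator: patients with at least one paired open-label reading.
2. Add a treatment-emergent row, restricted to patients whose paired reading at the SAP baseline (before the first lead-in dose) does not meet the criterion and who have at least one paired open-label reading.
3. Add the percentage meeting the criterion at baseline and at each visit, with the number of paired readings.
4. If paired readings were not taken at the lead-in baseline, say so, label the crude rate as not treatment-emergent, and show the Visit 1 and by-visit percentages with a note that some Visit 1 patients may already be on lumateperone.

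The cost is SAP wording and one extra table. The open-label readings are already scheduled; whether the baseline ones exist has to be checked against the lead-in studies. The downside is that baseline-positive patients leave the treatment-emergent denominator, but they stay in the crude row and the listing.

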10.4 Electrocardiograms

Descriptive statistics for ECG parameters (eg, ventricular heart rate, QTc interval, QRS interval) at baseline and changes from baseline values at each assessment visit, and at the end of the Openlabel Treatment Period will be summarized.

ECG parameter values will be considered PCS if they meet the criteria listed in Table 10-5. The number and percentage of patients with PCS postbaseline values during Open-label Treatment Period will be tabulated for the Safety Population. The percentages will be calculated relative to the number of patients with baseline value (for criteria involving change from baseline) or non-PCS baseline value (for criteria not involving change from baseline), and at least 1 assessment during the open-label treatment period. The numerator will be the total number of patients out of those included in the denominator and with at least 1 PCS value during the Open-label Treatment Period. A supportive listing for all patients with PCS values will be provided, which will include the PID number and baseline and postbaseline ECG values for each patient. A listing of all AEs for patients with PCS ECG values will also be provided.

Confidential Page 23 of 40

^a A postbaseline value will be considered potentially clinically significant if it meets both criterion value and change from baseline.

b Weight change is relative to baseline.

Table 10-5: Criteria for Potentially Clinically Significant Electrocardiographic Values

D	Criteria ^a							
Parameter, unit	Value	Change from Baseline						
QRS duration, msec	≥ 150	_						
PR interval, msec	≥ 250	_						
QTcB, msec	≥ 480	_						
QTcB, msec	≥ 500	_						
QTcF, msec	≥ 480	_						
QTcF, msec	≥ 500	_						
QTcB, msec	_	> 30 and ≤ 60						
QTcB, msec	_	Increase of > 60						
QTcF, msec	_	> 30 and ≤ 60						
QTcF, msec	_	Increase of > 60						

PCS = potentially clinically significant; QTc = corrected QT interval; QTcB = QT interval/(RR)½; QTcF = QT interval/(RR)½.

Confidential Page 24 of 40

^a A post-baseline value will be considered potentially clinically significant if it meets the criterion value or the change from baseline value.

10.5 Other Safety Parameters

10.5.1 Abnormal Involuntary Movement Scale (AIMS)

Descriptive statistics for AIMS total score at baseline and changes from baseline at each assessment visit (including the end of the Open-label Treatment Period) will be presented for the Safety Population.

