1. PROTOCOL SYNOPSIS AND SCHEDULE OF EVALUATIONS

CLINICAL STUDY SYNOPSIS:	Study ITI-007-503
Title of Study	An Open-label, Multicenter Trial to Assess the Safety and Tolerability of Lumateperone as Adjunctive Therapy in the Treatment of Patients with Major Depressive Disorder
Study Centers (Country)	Approximately 120 study centers (US and Non-US)
Development Phase	Phase 3
Objectives	Primary Objective To evaluate the safety and tolerability of lumateperone 42 mg administered orally once daily for approximately 26 weeks as adjunctive treatment to antidepressant therapy (ADT) in patients with major depressive disorder (MDD). Secondary Objectives To evaluate whether lumateperone 42 mg administered orally once daily for approximately 26 weeks as adjunctive treatment to ADT improves or maintains improvement of depressive symptoms in patients with MDD as measured by change from baseline in the Montgomery-Åsberg Depression Rating Scale (MADRS) total score and in the Clinical Global Impression Scale-Severity (CGI-S) score.
Study Design	This is an international, multicenter, open-label, fixed dose, 26-week study of patients with MDD. Eligible patients from the lead-in studies will enter the Open-label Safety Study at the Screening/Baseline Visit (Visit 1/Day 1), at which point patient eligibility will be assessed and informed consent obtained. At the Screening/Baseline Visit (Visit 1/Day 1), which is the same visit as Visit 8/Day 43 of the lead-in study, eligible patients will receive open-label lumateperone 42 mg once daily for approximately 26 weeks. Patients will continue their background ADT from the lead-in study. Patients will be seen for weekly visits through Visit 5/Week 4. Thereafter, visits will occur every two weeks. A Safety Follow-up visit will occur on Visit 17/Day 197, approximately 2 weeks after the last dose of open-label lumateperone 42 mg.
Number of Patients	Approximately 760 patients are planned to be enrolled in the Open-label Safety Study. No de novo patients will be enrolled.

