8.2.7.2 Extrapyramidal Scales

8.2.7.2.1 Abnormal Involuntary Movement Scale

The AIMS (Guy 1976) measures facial and oral movements, extremity movements, and trunk movements. Seven items are rated on a scale from none (0) to severe (4). A score of "mild" in 2 or more categories or a score of "moderate" or "severe" in any 1 category results in a positive AIMS score (ie, the scores are not averaged). Additionally, overall severity is scored on the basis of severity of abnormal movements and incapacitation due to abnormal movements. The patient's awareness of and distress caused by the abnormal movements are also noted. There are an additional 2 items on dental status that are answered yes or no. The AIMS is to be completed at Screening/Baseline (Visit 1/Day 1) and Visits 2, 5, 7, 9, 11, 13, 15, and 16/ET as specified in the Schedule of Evaluations (Table 1-1).

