9. STATISTICAL METHODS

9.1 General Considerations

The statistical analysis plan (SAP) will be finalized prior to database lock and will include a more technical and detailed description of the statistical analyses described in this section. This section is a summary of the planned statistical analyses of important endpoints including primary and key secondary endpoints.

Continuous variables will be summarized using descriptive statistics (number of patients [n], mean, standard deviation [SD], median, minimum, and maximum, unless otherwise stated). Categorical variables will be summarized using frequency counts and percentages.

The baseline for each specific efficacy/safety change-from-baseline analysis endpoint is defined as the last measurement prior to the first dose of study treatment from the lead-in study.

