9.4.5.5 Other Safety Parameters

Descriptive statistics for change from baseline to assessment visit and to the end of the Open-label Treatment Period in AIMS total score, BARS total score, and SAS total score will be summarized based on the Safety Population.

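### The protocol defines a positive AIMS for the individual patient, but neither its analysis section nor the SAP counts the patients who become positive

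*SAP*

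**What the plan says.** Protocol 8.2.7.2.1 has seven movement items rated from 0 to 4. It calls a patient positive when at least two categories are mild, or when any one is moderate or severe (in the protocol's words, this "results in a positive AIMS score (ie, the scores are not averaged"). AIMS is rated at Visit 1 and at eight later visits, ending with Visit 16/ET.

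The analysis text does not take the rule up. Protocol 9.4.5.5 says of change from baseline: "in AIMS total score, BARS total score, and SAS total score will be summarized". SAP 10.5.1 plans "Descriptive statistics for AIMS total score at baseline and changes from baseline at each assessment visit", including the end of open-label treatment. Protocol 9.1 lists what such a summary contains: "number of patients [n], mean, standard deviation [SD], median, minimum, and maximum, unless otherwise stated".

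Three other provisions matter here.

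- **Baseline.** For safety measures, the opening paragraph of SAP Section 10 states: "Baseline is defined as the last measurement prior to the first dose of double-blind treatment during the lead-in studies".
- **Patient counts elsewhere.** The SAP counts patients with potentially clinically significant (PCS) laboratory, vital-sign and ECG values (10.2 to 10.4), orthostatic hypotension (10.3) and emergent suicidality (10.5.4).
- **Other views of abnormal movements.** SAP 10.1 tabulates extrapyramidal TEAEs by preferred term, and SAP 15.2 places all open-label assessments in data listings.

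**The concern.** The primary objective is safety and tolerability, and AIMS is the systematic rating of abnormal movements. An emerging movement disorder is something that happens to individual patients, and the protocol supplies a threshold for recognising it. A summary of total scores over the whole Safety Population answers a different question, namely how far the average rating moved.

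Without a count, the report could show almost no average change and could not say from the scale how many patients crossed the protocol's own threshold. Other safety measures with a threshold in this plan do get such a count.

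**Working it through.** Neither document states a figure for AIMS, and the sample size is not based on power, so there is no planned number to reproduce. The checks ask what the planned table can show.

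**Inputs.** N = 760, from the protocol synopsis ("Approximately 760 patients are planned to be enrolled in the Open-label Safety Study"). This is planned enrolment, not the number with evaluable AIMS. The seven items scored 0 to 4 come from Protocol 8.2.7.2.1.

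**Assumptions.** The documents give only the end anchors and do not define the total. I take 1 = minimal, 2 = mild, 3 = moderate; the total as the sum of the seven items (0 to 28); and categories to mean items. The documents give no AIMS data, so the case numbers and sizes of rise are illustrative.

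**Check 1: does the total determine AIMS status?**

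- Smallest positive total: one item at moderate = 3 (two items at mild = 4).
- Largest negative total: one item at mild and six at minimal = 2 + 6 × 1 = 8.
- So totals of 0 to 2 are always negative, 9 or more always positive, and 3 to 8 can be either.

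Enumerating all 5^7 = 78,125 item patterns confirms this. The figures count patterns and are not probabilities.

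| Total | Negative | Positive |
|---|---|---|
| 3 | 77 | 7 |
| 4 | 140 | 70 |
| 5 | 161 | 294 |
| 6 | 112 | 763 |
| 7 | 43 | 1,477 |
| 8 | 7 | 2,408 |

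**Check 2: what do the summary statistics show?** If k patients rise by d points and the rest do not change, the mean change is k × d / N. For k = 8 and d = 3 this is 24/760 = 0.032.

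| k (% of 760) | d | Mean | SD | Median | Maximum |
|---|---|---|---|---|---|
| 4 (0.5%) | 3 | 0.016 | 0.22 | 0 | 3 |
| 8 (1.1%) | 3 | 0.032 | 0.31 | 0 | 3 |
| 8 (1.1%) | 4 | 0.042 | 0.41 | 0 | 4 |
| 15 (2.0%) | 3 | 0.059 | 0.42 | 0 | 3 |
| 15 (2.0%) | 6 | 0.118 | 0.84 | 0 | 6 |

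Modest improvement elsewhere can cancel the mean. Eight patients at +4 and 32 at −1 give (32 − 32)/760 = 0, with the maximum still 4.

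**Check 3: can one table fit different numbers of cases?** Suppose 8 patients go from none to moderate on one item: each rises 3 points and is positive. Suppose instead that 8 patients go from none to minimal on three items: each again rises 3 points, and none is positive. With everyone else unchanged, n, mean (0.032), SD (0.31), median (0), minimum (0) and maximum (3) are the same. The number of positive patients is 8 in the first case and 0 in the second.

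**The case against.** Several stronger readings are tempting, and the documents do not support them.

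- **That only the mean is reported.** Protocol 9.1 adds SD, median, minimum and maximum. A high maximum at a visit shows that at least one patient worsened.
- **That the plan cannot show new dyskinesia.** SAP 10.1 tabulates extrapyramidal TEAEs. Dyskinesia is on the narrow list, and an abnormal AIMS is itself a term on the broad list. Patients are asked about adverse events at every visit, and SAP 15.2 lists all assessments.
- **That the SAP departs from the protocol.** Protocol 9.4.5.5 plans the same total-score summary. The gap lies between two sections of the protocol, and the SAP inherits it.
- **That the protocol forbids averaging.** The remark in 8.2.7.2.1 concerns combining items within one patient. It does not rule out group means of a total score.
- **That the shift would be lost in noise.** In the 8-case illustration the SD is 0.31, so the standard error is 0.31/√760 = 0.011 and the shift is nearly three standard errors. At one decimal, 15 cases (0.059) would print as 0.1. The difficulty is that the mean does not translate into a number of patients.
- **That movement disorders are the stated reason for 26 weeks.** Protocol 6.2.1 cites chronic, relapsing illness and general safety, tolerability and efficacy data.

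All of this stands, but it does not supply the missing count. The maximum does not say how many patients worsened or whether any met the rule. TEAEs are elicited with a nonleading question (Protocol 8.2.1.4) and need an investigator to report an event. Listings are not summaries. For repeated or unscheduled AIMS, SAP 15.2 keeps the last value in a window, so a positive rating followed by a lower repeat drops out of the visit table. SAP 15.2 does bring every assessment into PCS determination, but AIMS has no PCS criterion.

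**Conclusion.** The concern holds as an omission in both documents: a patient-level definition is given and never analysed. It is neither a contradiction between the documents nor a complete inability to detect cases.

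Its size can only be illustrated. For 4 to 15 new cases among 760 (0.5% to 2.0%), with rises of 3 to 6 points and no other change, the mean change is 0.016 to 0.118 and the median 0. The result that totals of 3 to 8 leave status open rests on the assumed anchors, on the total being the item sum, and on categories meaning items.

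The point is confined to AIMS, because the protocol writes no comparable positive threshold for the BARS or SAS. The addition is worth making: it changes what the study can conclude about abnormal movements.

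**What to change.** In SAP 10.5.1, keep the total-score table and add:

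1. The number and percentage of patients with a treatment-emergent positive AIMS, meaning the protocol rule is met at any assessment after the first open-label dose, including unscheduled ones. Show the same separately at the end of open-label treatment.
2. A denominator of patients not positive at baseline who have at least one open-label AIMS.
3. Both counts relative to the SAP's pre-lead-in baseline, and again relative to open-label Day 1. Protocol 6.2.1 says patients may start or continue lumateperone, and the pre-lead-in baseline alone would count conversions during the lead-in study as arising in the open-label period.
4. A listing of positive patients with their item scores by visit.
5. One sentence stating which item scores are mild, moderate and severe, that categories means items (if so), and how the total is formed.

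The cost is one table and one listing from ratings the protocol already collects, plus baseline item scores carried over from the lead-in studies. No new assessment or visit is needed.
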